## **12 STATISTICAL METHODS AND CONSIDERATIONS**

Prior to the analysis of the final study data, a detailed Statistical Analysis Plan (SAP) will be written describing all analyses that will be performed. The SAP will contain any modifications to the analysis plan described below.

### **12.1 Data Sets Analyzed**

All eligible patients who are randomized into the study and receive at least one dose of the study drug (the Safety Population) will be included in the safety analysis.

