TEST PRODUCT, DOSE, AND ROUTE OF ADMINISTRATION	fMRI phase: Single dose 40 IU of intranasal oxytocin  Longitudinal phase: Twice-daily for approximately 3 weeks (18- 24 days) of 40 IU of intranasal oxytocin
CONTROL PRODUCT, DOSE AND ROUTE OF ADMINISTRATION	fMRI phase: Single dose of intranasal placebo  Longitudinal phase: Twice-daily for approximately 3 weeks (18-24 days) of intranasal placebo
DURATION OF SUBJECT PARTICIPATION AND DURATION OF STUDY	
Subjects will be on study for up to 42 days
 
Screening: The investigators will contact subjects to conduct a phone screening interview to verify eligibility. Screening will take at most twenty minutes. In order to reduce number of in-person visits, Visit 1 has been adapted to be completely remote. Participants will verbally consent at the start of Visit 1, before completing any study tasks or assessments. Clinical diagnosis will be obtained prior to participation and will take up to 4 hours.
 
Written informed consent will be obtained during Visit 2, the first in-person visit, before study drug administration.
 
Treatment: Subjects will participate in the study for up to 7 weeks. The first two visits will be separated by at least 1 week. The third and fourth visit will be separated by at least 3 weeks (18-24 days). Each visit will be between one to four hours.
 
The total duration of the study is expected to be 5 years. 54 months for subject recruitment.

CONCOMITANT MEDICATIONS	
Allowed: atypical antipsychotic medication of a consistent, therapeutic dose
 
Prohibited: high dose testosterone or estrogen/progesterone

EFFICACY EVALUATIONS	The epidemiologist will be evaluating social functioning at multiple points throughout the study to determine the drug treatment arm with greater improvement which will then be implemented in the RAR design. Results will remain blinded to the study staff.
PRIMARY ENDPOINT	
 
• Neural activity from fMRI
 

	
 
• Social Functioning Scale (SFS)
 

SECONDARY ENDPOINTS	
 
• Social Skills
 
• Negative Symptoms
 
• Theory of Mind
 

OTHER EVALUATIONS	

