### **4 STUDY DESIGN**

#### **4.1 Study Overview**

100 subjects are planned. During the fMRI phase, intranasal oxytocin and placebo will be administered to each subject in a randomized, double-blind, counterbalanced order with a cross-over design, at least one week apart. Testing will commence 45 minutes after drug administration and continue for no longer than 3 hours.

During the longitudinal phase, participants will then be randomized to receive approximately three weeks (18-24 day range) of twice daily administration of either OT or placebo. Testing will commence on baseline and after three weeks (18 to 24 days) of drug administration.

Screening data will be reviewed to determine subject eligibility. Subjects who meet all inclusion criteria and none of the exclusion criteria will be entered into the study.

The following treatment regimens will be used:

- Experimental treatment: Intranasal oxytocin
- Placebo: Saline solution

Total duration of subject participation will be 15 hours over 2 months.

---

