## 8 STUDY TREATMENTS

### 8.1 Method of Assigning Subjects to Treatment Groups

Randomization sequences will be generated using a response adaptive randomization study design. Enrollment would end when at least 55 participants have been assigned to the drug treatment arm and 40 participants have been assigned to the placebo arm.

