### **9.1.7 Adverse Events**

Information regarding occurrence of adverse events will be captured throughout the study. Duration (start and stop dates and times), severity/grade, outcome, treatment and relation to study drug will be recorded on the case report form (CRF).

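### The Safety Population is limited to eligible patients, so read literally it leaves out anyone dosed and later found ineligible; adverse events also need a phase-and-product rule (minor)

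*Combined protocol and SAP*

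**What the plan says.** Section 12.1 holds the only analysis-set definition in the document. The safety analysis includes "All eligible patients who are randomized into the study and receive at least one dose of the study drug". It does not say whether events are summarised by assigned arm, by product received or by phase.

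On exposure, section 4.1 states that in the fMRI phase "intranasal oxytocin and placebo will be administered to each subject in a randomized, double-blind, counterbalanced order with a cross-over design". The synopsis gives the acute active treatment as "fMRI phase: Single dose 40 IU of intranasal oxytocin". After that, "participants will then be randomized to receive approximately three weeks (18-24 day range) of twice daily administration of either OT or placebo".

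On entry, section 4.1 states: "Subjects who meet all inclusion criteria and none of the exclusion criteria will be entered into the study". On data, section 9.1.7 has events captured throughout the study and specifies for the case report form: "Duration (start and stop dates and times), severity/grade, outcome, treatment and relation to study drug will be recorded". Section 12 says that a detailed SAP will be written before the final data are analysed and may modify the plan.

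**The concern.** A safety set normally holds everyone exposed, because a mistake at screening does not undo an exposure. Under the wording of section 12.1, a participant whose ineligibility comes to light after dosing does not meet the definition. Several exclusions in section 6.3 bear on tolerability, for example significant medical disorder, high-dose hormones, and congestion or sinus problems. The last overlaps with the nasal effects that section 5.3 expects. Leaving out even a few such participants would make the safety summary incomplete in the people for whom it may be most informative.

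The second matter is a missing detail. Because the fMRI phase is a cross-over, the longitudinal arm label does not describe a participant's whole exposure: someone assigned to longitudinal placebo has normally already had one dose of oxytocin. The only treatment variable in section 12 is the two-level drug-versus-placebo indicator of section 12.3. If that label were also used for all adverse events from Visit 2 onward, acute oxytocin events would appear in the placebo column. Such a table would also have no natural place for participants who leave before Visit 4.

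**Working it through.** The plan states no figure on this point, so there is none to reproduce. The check has three parts.

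**1. Who falls outside the set.** Section 12.1 requires three things: eligible, randomized, and at least one dose. Section 4.1 admits only those who meet the criteria, which makes ineligible dosing uncommon. It does not cover ineligibility discovered afterwards, and no section says how such a participant is classified. The documents give no rate. As an assumption, for 100 dosed participants ("100 subjects are planned"):

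| Assumed share later found ineligible | Left out under a literal reading | Left out if *eligible* is deleted |
|---|---|---|
| 1% | 1 | 0 |
| 3% | 3 | 0 |
| 5% | 5 | 0 |
| 10% | 10 | 0 |

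**2. Exposure by longitudinal arm.** Section 8.1 ends enrolment when "at least 55 participants have been assigned to the drug treatment arm and 40 participants have been assigned to the placebo arm". At that minimum, 55 + 40 = 95. If all 95 completed the fMRI phase, all 95 have had oxytocin, and the longitudinal label calls 40/95 = 42% of them placebo. With 100 participants split 60/40 or 55/45, the share is 40% or 45%.

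**3. What a whole-study table by longitudinal arm would show.** Let *a* be the risk of an event from the acute oxytocin dose (the same in both arms by design), *c* the longitudinal risk on oxytocin and *b* the longitudinal risk on placebo. Assume independence and, for simplicity, no added risk from the acute placebo dose. Then:

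- risk in the oxytocin arm = 1 − (1 − *a*)(1 − *c*)
- risk in the placebo arm = 1 − (1 − *a*)(1 − *b*)
- risk difference = (1 − *a*)(*c* − *b*)

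The documents give no event rates, so all of these are assumed:

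| *a* | *c* vs *b* | Whole-study risks | Risk ratio | Risk difference |
|---|---|---|---|---|
| none | 15% vs 5% | 15.0% vs 5.0% | 3.0 | 10 points |
| 5% | 15% vs 5% | 19.25% vs 9.75% | 1.97 | 9.5 points |
| 10% | 15% vs 5% | 23.5% vs 14.5% | 1.62 | 9.0 points |
| 20% | 15% vs 5% | 32.0% vs 24.0% | 1.33 | 8.0 points |
| none | 20% vs 10% | 20.0% vs 10.0% | 2.0 | 10 points |
| 5% | 20% vs 10% | 24.0% vs 14.5% | 1.66 | 9.5 points |
| 10% | 20% vs 10% | 28.0% vs 19.0% | 1.47 | 9.0 points |
| 20% | 20% vs 10% | 36.0% vs 28.0% | 1.29 | 8.0 points |

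In a placebo arm of 40, the expected number of acute oxytocin events is 40*a* = 2, 4 or 8. The risk ratio falls markedly, while the risk difference shrinks only by the factor (1 − *a*). The acute contrast itself does not appear, because *a* is common to both columns.

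**The case against.** Section 12.1 sets membership; it does not describe removing anyone. Since section 4.1 enters only participants who meet the criteria, *eligible* may simply mean those who passed screening. Use of prohibited hormones during the study is treated as a protocol violation (section 7.2), and a protocol violation may lead to stopping treatment (section 11.1). Neither section takes the person out of the safety set. This stands as a possible reading, but the sentence does not say so, and a literal reader would apply the condition as written.

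A reader might infer that events in ineligible participants are lost altogether. The documents do not support that: section 9.1.7 records events throughout the study, so they would be absent from one analysis set and not from the record.

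A reader might also infer that the plan credits oxytocin events to placebo. It does not. No section plans a table by longitudinal arm, section 5.3 describes no comparison between arms, the dates and times recorded allow events to be placed by phase, and section 12 defers detail to a later SAP. What stands is that no attribution rule is written yet, in a design where the arm label alone is not enough.

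Finally, it would be too strong to say that every participant receives oxytocin. Someone who leaves after a placebo-first Visit 2 never does.

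**Conclusion.** The point holds as a minor one. The word *eligible* in section 12.1, followed literally, leaves a dosed participant later found ineligible out of the safety analysis. How many this would affect is unknown; 1 to 10 of 100 is the range under assumed rates of 1% to 10%, and the entry rule in section 4.1 makes it uncommon.

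The attribution matter is a clarification for the later SAP and not an error in a stated analysis. If a whole-study table by longitudinal arm were used, it would hide the acute oxytocin-placebo contrast and reduce risk ratios (3.0 to between 1.97 and 1.33, or 2.0 to between 1.66 and 1.29). A reader might conclude that the difference between arms would be substantially diluted. On the risk-difference scale that is not so: 10 points becomes 9.5, 9.0 or 8.0. All these figures rest on assumed event rates, independence of the two phases, and no added risk from the acute placebo dose.

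**What to change.** 1. In section 12.1, delete *eligible* and define the safety set as everyone who received at least one dose of oxytocin or placebo. Naming both products also removes an ambiguity: the synopsis statistics entry sets study drug against placebo, while the study-drug administration row in Appendix 1 covers both.
2. In the SAP, before unblinding, state that adverse events are summarised by phase and by product actually received. Give a rule for events that start between the two cross-over sessions; attribution to the most recent product is one reasonable convention. Count longitudinal events from the first longitudinal dose at Visit 4.
3. Confirm that onset dates and times are collected at each contact as section 9.1.7 implies. The lists for Visits 1 to 5 do not name adverse events, and that row of Appendix 1 shows no visit marked in the text available.

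The cost is a change of wording and one table layout. No data items beyond those in section 9.1.7 are needed.

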### **12.2 Demographic and Baseline Characteristics**

### **12.3 Analysis of Primary Endpoint**

The investigators will perform linear regression analyses with SFS change as the primary outcome and drug modeled as a 2-level dummy variable (drug vs. placebo). Identical analyses will be run using accuracy scores for the FBT and PDT instead of rTPJ activity to determine if acute OT improves ToM ability versus placebo.

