STUDY DESIGN	This is a double-blind, placebo-controlled, counterbalanced order with a cross-over design one week apart, followed by a randomized,

	double-blind, three week (18-24 days) study design. We will also be implementing a response adaptive randomization (RAR) design after the first 60 participants complete the study. This will change the allocation ratio to favor the drug treatment arm with greater improvement in social functioning, while keeping adequate statistical power in all arms.
PRIMARY OBJECTIVE	The objective is to clarify how and in whom exogenous oxytocin improves social functioning in schizophrenia as measured by acute neural response patterns during social cognitive tasks and social functioning as measured by the Social Functioning Scale (SFS).
SECONDARY OBJECTIVES	
Social skills will be assessed during the chronic period over the phone or video chat. Participants will answer questions about their social interactions and experiences.
 
Theory of Mind (ToM) will be assessed using the Hinting Task a well validated audiovisual tool that incorporates social interferences.
 
Negative symptoms will be assessed with Clinical Assessment Interview for Negative Symptoms (CAINS), comprising two subscales reflecting the negative symptom factors. Data will be analyzed with manual and computerized approaches.

NUMBER OF SUBJECTS	100 total participants
SUBJECT SELECTION CRITERIA	
Inclusion Criteria:
 
18-70 years of age; meet DSM-V criteria for schizophrenia, schizoaffective disorder or brief psychotic disorder; no medication changes or psychiatric hospitalizations in the past month; SFS raw score of no more than 75.
 
Exclusion Criteria:
 
Active substance use disorder in the past month except mild to moderate cannabis use disorder, schizoaffective, schizopreniform disorder, or brief psychotic disorder; DSM-5 diagnosis other than schizophrenia; Significant neurological/medical disorders; a pacemaker; extensive dental work; claustrophobia; deafness; inability

	to read; current participation in a psychosocial intervention; taking high dose testosterone, estrogen/progesterone. Currently pregnant, breastfeeding, or unwilling to practice birth control during participation.

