SAFETY EVALUATIONS	No serious adverse effects have been demonstrated in studies examining intranasal administration of OT in numerous patient and healthy populations. Therefore, we don't predict any serious adverse events to occur during this study. Documented side effects include runny, stuffy, or irritated nose, and more rarely, nausea and vomiting. Participants may experience distress due to the nature of personal questions about mental health, substance use, and life experiences. They may also experience anxiety and/or fatigue due to length of the study days.
PLANNED INTERIM ANALYSES	Interim analysis will be conducted after the first 60 participants have completed the study and at multiple points over the course of the study. Results will remain blinded to all other study staff.
STATISTICS Primary Analysis Plan	
Linear regression analyses with SFS change and rTPJ activation as the primary outcomes and drug modeled as a 2-level dummy variable comparing the study drug vs. placebo.
 
Similar analyses will be conducted for the secondary clinical outcomes including social ability, negative symptoms (CAINS and Theory of Mind (HintingTask).

Rationale for Number of Subjects	All power and effect size estimates were calculated using STATA/SE v. 15.1 using 80% power and two-sided alpha=0.05. To be conservative, the investigators used the one-way command with two or three groups. The proposed sample size of 100 participants enables us to detect effect sizes of 0.23 for the primary hypotheses, which is clinically meaningful.

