### **3 STUDY OBJECTIVES**

#### **3.1 Primary Objective**

The primary objective is to clarify how and in whom oxytocin improves social functioning in schizophrenia. The study will assess the effects of exogenous oxytocin on social functioning, as measured by the Social Functioning Scale (SFS). Neural activation patterns, as measured will be measured by fMRI rTPJ responses during well-characterized social cognitive tasks. This will help determine if acute fMRI rTPJ responses to single oxytocin administration predicts clinical responses to chronic oxytocin treatment in schizophrenia participants.

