### **12.4 Analysis of Secondary Endpoints**

Similar analyses as stated in 15.3 will be conducted for the secondary clinical outcomes including social ability, negative symptoms (CAINS), and ToM(Hinting Task).

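### The SFS-change regression leaves its standard error to the equal-variance default although the arms are planned unequal; an unequal-variance standard error would be better at almost no cost (minor).

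*Combined protocol and SAP*

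**What the plan says.** Section 12.3 gives the primary analysis in one sentence: "The investigators will perform linear regression analyses with SFS change as the primary outcome and drug modeled as a 2-level dummy variable". The synopsis repeats the model and adds the imaging outcome: "Linear regression analyses with SFS change and rTPJ activation as the primary outcomes and drug modeled as a 2-level dummy variable". Neither place says how the standard error is obtained. Section 12.4 extends the model: "Similar analyses as stated in 15.3 will be conducted for the secondary clinical outcomes". No Section 15.3 appears in the protocol, so I read this as 12.3; the outcomes it covers are social ability, CAINS and the Hinting Task.

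On arm sizes, the synopsis says of the adaptive randomization after the first 60 completers: "This will change the allocation ratio to favor the drug treatment arm with greater improvement in social functioning". Section 8.1 stops enrolment once "at least 55 participants have been assigned to the drug treatment arm and 40 participants have been assigned to the placebo arm". The planned total is 100 (synopsis and Section 4.1).

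On varying response, Section 3.1 states: "The primary objective is to clarify how and in whom oxytocin improves social functioning in schizophrenia". It also asks whether "acute fMRI rTPJ responses to single oxytocin administration predicts clinical responses to chronic oxytocin treatment".

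Section 12 defers a detailed SAP to a time before the final analysis. No SD of SFS change, arm-specific variance or responder share is given anywhere.

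**The concern.** With drug as the only term, ordinary linear regression is the two-sample t-test with a pooled variance. In equal arms, unequal variances do almost no harm to that test. In unequal arms the pooled standard error is biased: too large when the bigger arm is the more variable one, too small when the smaller arm is.

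This trial departs from equal arms by design. Its primary objective also makes unequal variances plausible, because patients who differ in their response to oxytocin add spread to the drug arm that the placebo arm lacks. At stake are the width of the confidence interval for the SFS effect and some power, in the very scenario the trial is set up to study. The same holds for the secondary clinical outcomes. It does not concern the imaging phase, where each participant receives both treatments.

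**Working it through.** **The plan's own figures.** The documents contain no variance figure to reproduce. The only related numbers are the detectable effects of 0.23 to 0.27 (Section 12.6), from a one-way method that also assumes a common variance. They do not reproduce as the effect size f with two groups at N = 100, which gives 0.283. That is a separate matter, and nothing below depends on it.

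**Inputs.** From the documents: at least 55 on drug and 40 on placebo, planned total 100, two-sided alpha 0.05. Assumed: the drug:placebo variance ratio (VR), shown mainly at 1.5 and 2; normal errors unless stated; fixed arm sizes.

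**Arm sizes possible at N = 100.** With drug ≥ 55 and placebo ≥ 40, drug is 55 to 60 and placebo is 45 to 40. Drug is always the larger arm. For placebo to be larger while drug has at least 55, the total must exceed 55 + 55 = 110.

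**Formula.** With placebo variance 1 and drug variance VR, the pooled SE divided by the true SE is

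R = sqrt{ [((nD−1)VR + (nP−1)) / (nD+nP−2)] × (1/nD + 1/nP) / (VR/nD + 1/nP) }.

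Example, 55/40 with VR 2:
- pooled variance = (54×2 + 39)/93 = 1.5806
- pooled SE² = 1.5806 × 0.04318 = 0.06826
- true SE² = 2/55 + 1/40 = 0.06136
- R = sqrt(0.06826/0.06136) = 1.055

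For an effect of 2.8 true SEs (about 80% power), power is approximately Φ(2.8 − 1.96R). At R = 1 this is Φ(0.84) = 80.0%. Interval coverage is approximately 1 − 2[1 − Φ(1.96R)].

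| Drug/placebo | VR | R | Power, pooled | Loss from 80.0% | 95% CI coverage |
|---|---|---|---|---|---|
| 55/45 | 1.5 | 1.020 | 78.8% | 1.2 | 95.5% |
| 55/45 | 2 | 1.034 | 78.0% | 2.0 | 95.7% |
| 55/40 | 1.5 | 1.032 | 78.1% | 1.9 | 95.7% |
| 55/40 | 2 | 1.055 | 76.8% | 3.2 | 96.1% |
| 60/40 | 1.5 | 1.041 | 77.6% | 2.4 | 95.9% |
| 60/40 | 2 | 1.070 | 75.9% | 4.1 | 96.4% |

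Simulation with t critical values puts every power figure about a point lower but gives the same losses. At 60/40 with VR 2, for example, power is 75% pooled against 79% Welch. Welch held its size at 4.9 to 5.1% in every scenario run.

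**Responder mixtures (assumed).** If a share q gains e placebo SDs, VR = 1 + q(1−q)e².
- 30% gaining 2 SD: VR = 1 + 0.21×4 = 1.84. At 55/40, simulated power is 65.9% pooled and 69.3% Welch.
- 50% gaining 1 SD: VR = 1 + 0.25 = 1.25. At 55/40, simulated power is 60.6% pooled and 61.9% Welch.

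**When the error goes the other way.**
- Placebo the more variable arm, 55/40, drug/placebo SD ratio 0.67: R = 0.940, rejection rate 6.6%.
- Placebo the larger arm, VR 2: 5.4% at 55/60 (115 enrolled) and about 6.3% at 55/75 (130 enrolled).

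**No effect in any patient.** Response adds no variance, and the pooled test rejects 5.0% of the time.

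**The case against.** **The documents do not say the variance is pooled.** This stands. They are silent, and a SAP is still to come. The point is that the named model has a default and nothing overrides it. It is not that a wrong method was chosen.

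**A reader might infer an inflated false-positive rate, or an error whose direction depends on the interim results, because the adaptive step could favour placebo.** The documents do not support that for the trial as planned. An end state such as 40 drug/60 placebo breaks the Section 8.1 minimum of 55 on drug, and at 100 participants the drug arm is always the larger. With extra variance on oxytocin, the error is conservative. Inflation would need a more variable placebo arm, or enrolment past about 110 with placebo the larger arm, and it would then be modest.

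**A reader might also treat the altered rejection rates as type I error in the usual sense.** If the extra variance comes from response and nobody responds, the variances are equal and the test is valid. If some respond and none are harmed, the mean effect is positive and rejection is correct. An altered rejection rate at zero average effect needs benefit and harm to cancel, which no section suggests. What remains is interval width and power.

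**The variances are assumed, and asking in whom a drug works is not the same as stating that only some respond.** Both are true. With VR 1.25 the loss at 55/40 is about 1 point, and at 55/45 it is smaller still. Against that, the Welch method costs almost nothing if the premise fails.

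**All figures hold arm sizes fixed.** This stands. They do not show calibration under adaptive allocation or repeated interim looks.

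**Conclusion.** The concern holds as a minor point of analysis choice. The primary regression defaults to a common variance in a trial planned with unequal arms. Under an assumed variance ratio of 1.5 to 2 with the drug arm the more variable, the standard error is about 3 to 7% too large at 55/40 to 60/40, and power falls by about 2 to 4 points. At 55/45 the standard error is about 2 to 3% too large and the loss is about 1 to 2 points. Coverage of the 95% interval is about 95.5 to 96.4% over these splits.

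The error is conservative at the planned N, and there is none if oxytocin affects nobody. The size rests on variance ratios that the documents do not give, on fixed arm sizes and on approximately normal errors. The case for acting is that a better-calibrated method is available for almost nothing, and that it should be named before the SDs by arm are seen.

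**What to change.** In Section 12.3, and in the SAP when it is written, keep the linear regression and the drug coefficient. Add that the standard error, confidence interval and p-value use the unequal-variance (Welch) method, that is, HC2 standard errors with Satterthwaite degrees of freedom. Report the SD of SFS change by arm beside the estimate. Section 12.4 then inherits this for the secondary outcomes, once its reference to 15.3 is corrected.

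The cost is one sentence and one software option, with no extra patients or data. If the variances are equal, about 0.1 point of power is lost. HC3 is a workable alternative but is not the Welch test: with drug as the only term its variance is s²/(n−1) per arm, where Welch uses s²/n. HC3 is slightly more conservative and costs about 0.5 to 0.6 point under equal variances.

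This change does not deal with the adaptive allocation or the repeated interim looks, which need their own provisions.

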### 6.2 Inclusion Criteria

1. Veteran
2. Male or female  $18 \geq 70$  years of age at Visit 1.
3. Must comprehend English
4. Meet DSM-V criteria for schizophrenia, schizophreniform, schizoaffective disorder, or brief psychotic disorder.
5. Clinically stable, no medication changes or psychiatric hospitalizations in past month
6. Social Functioning Scale raw score  $\leq 75$
7. Written informed consent obtained from subject or subject's legal representative and ability for subject to comply with the requirements of the study.

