## 8.2 Blinding

Due to the objectives of the study, the identity of test and control treatments will not be known to investigators, research staff, or participants. The following study procedures will be in place to ensure double-blind administration of study treatments.

- Access to the randomization code will be strictly controlled.
- Packaging and labeling of test and control treatments will be identical to maintain the blind. The oxytocin or placebo will be repackaged into smaller bottles containing 1 mL of either the oxytocin or placebo. Designated study staff, who will not be present during the study sessions and will not be involved with running any of the study sessions, will be responsible for repackaging the drugs and keeping track of each bottle's contents for unblinding.

The study blind will be broken on completion of the clinical study and after the study database has been locked.

- Investigators will be made aware of their subject treatment assignments at the completion of the study.

During the study, the blind may be broken **only** in emergencies when knowledge of the participant's treatment group is necessary for further participant management. When possible, the Investigator should discuss the emergency with the Medical Monitor prior to unblinding. During the study, the blind may be broken to the designated unblinded study staff **only** in emergencies when knowledge of the participant's treatment group is necessary for further participant management.

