### **12.5 Interim Analysis**

Interim analysis will be conducted after the first 60 participants have completed the study and at multiple points after over the course of the study. Results will remain blinded to all other study staff.

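### The primary SFS regression names only drug although allocation will follow interim results; a pre-specified allocation-period term, baseline SFS and named SFS visits are a cheap improvement

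*Combined protocol and SAP*

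**What the plan says.** Section 12.3 describes "linear regression analyses with SFS change as the primary outcome and drug modeled as a 2-level dummy variable (drug vs. placebo". The statistics entry of the synopsis gives the same form, with "drug modeled as a 2-level dummy variable comparing the study drug vs. placebo". No term for enrolment period, randomisation block or baseline SFS is named anywhere.

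The synopsis introduces response-adaptive randomisation after 60 completers: "This will change the allocation ratio to favor the drug treatment arm with greater improvement in social functioning". Section 12.5 places interim analyses "after the first 60 participants have completed the study and at multiple points after over the course of the study". Section 8.1 ends enrolment when "at least 55 participants have been assigned to the drug treatment arm and 40 participants have been assigned to the placebo arm". No starting ratio, later ratio or updating rule is given. The synopsis allows "54 months for subject recruitment".

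On the measurement of SFS change:
- Sections 4.1 and 5.1 refer to a baseline without giving a visit number.
- Section 10.1 lists social functioning assessments at Visit 1.
- Sections 10.4 and 10.6 list social ability, with ToM and symptoms, at Visits 4 and 5.
- Section 10.5 lists a social functioning assessment in the remote chronic period.
- Appendix 1 marks social functioning tests at Visits 1, 4 and 5.

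Section 6.2 caps the "Social Functioning Scale raw score" at 75 for entry. Section 12 promises a detailed SAP, which may modify the plan, before the final data are analysed.

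**The concern.** Under adaptive allocation, the chance of receiving drug depends on when a participant is assigned. If SFS change also depends on when a participant is assigned, a model without calendar period mixes the two. The drift has to be in within-person change, because a shift in SFS level that affects both measurements cancels in the subtraction. Recruitment is long enough for such drift. In addition, section 10.1 says that Visit 1 became remote. If Visit 1 is the baseline and that switch falls within enrolment (it is not dated), a mode effect would touch only one end of the change score.

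Two smaller matters concern the same sentence of the plan. Baseline SFS enters only by subtraction, which is valid but usually less precise than using it as a covariate. And SFS change is not fully defined while neither of its visits is named: change from Visit 1 spans the two fMRI-phase doses, and change from Visit 4 does not.

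**Working it through.** The plan gives no figure for drift or for its effect, so there is none to reproduce. From the documents: the model (section 12.3), a change of ratio after 60 completers (synopsis), and minimum totals of 55 and 40 (section 8.1). Assumed: SD of SFS change 1, normal errors, exactly 60 participants before the ratio changes, and a step drift after them. Tests are two-sided at 5%. Power is taken at d = 0.566, the effect that 100 participants at 1:1 detect with 80% power. This does not rely on the plan's own effect sizes.

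**1. Fixed splits, all ending 55/40.** Bias = drift × (share of the drug arm assigned late − share of the placebo arm assigned late).

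| Split (drug:placebo, early then late) | Bias per unit drift | Type I, no drift | Type I, 0.5 SD step, either sign | Power, none / −0.5 / +0.5 |
|---|---|---|---|---|
| A: 30:30, 25:10 | 25/55 − 10/40 = 0.205 | 5.2% | 7.0 to 7.1% | 77 / 58 / 88% |
| B: 33:27, 22:13 | 22/55 − 13/40 = 0.075 | 5.0% | 4.6 to 4.8% | 77 / 69 / 80% |
| C: 35:25, 20:15 | 20/55 − 15/40 = −0.011 | 5.1% | 4.3 to 4.4% | 77 / 76 / 75% |

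In B and C the rate falls below 5% because an unmodelled step inflates the residual variance more than it biases the estimate. In A a 0.25 SD step gives 5.5 to 5.7%. With a period term, type I error is 4.8 to 5.2% throughout.

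**2. A response-driven rule.** Fixed splits leave out the dependence of later allocation on earlier results. One assumed rule that includes it: 30:30, then four blocks of 10, with the probability of drug equal to Φ(interim z) clipped to 0.25–0.75; N = 100, no drug effect. It does not enforce the section 8.1 counts. Ranges are over repeat runs of the rule, including a check with 8,000 trials per case.

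| Step drift (SD) | Type I, drug only |
|---|---|
| 0 | about 5% |
| +0.25 | 9 to 10% |
| +0.5 | 15.5 to 17% |
| −0.25 | 2 to 2.6% |
| −0.5 | 0.9% |

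With a period term it is 4.5 to 5.5% in every case. The sign matters. If late participants improve more, the arm that leads by chance receives more of them and its lead grows; if they improve less, the lead shrinks. In the 8,000-trial check the drug-only estimate averaged within 0.005 of zero in each case, so under this rule the fault lies in the error rate and not in average bias.

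**3. Cost of the period term with no drift.** Variance ratio = [1/Σ ab/(a+b)] ÷ (1/55 + 1/40), summed over periods with a on drug and b on placebo.
- A: (1/22.143)/0.04318 = 1.046; power goes from 77.1% to 75.1%.
- B: (1/23.021)/0.04318 = 1.006; power goes from 77.1% to 76.8%.
- C: 1.0001; power unchanged.

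**4. Gain from baseline SFS.** With baseline-to-final correlation r and equal variances, the ratio to the change score is (1−r²)/[2(1−r)] = (1+r)/2. With baseline SD k times the final SD it is (1−r²)/(1+k²−2kr). The entry limit of 75 could make k less than 1. At an assumed r = 0.6:
- k = 1: 0.64/0.80 = 0.80; times A's 1.046, 0.84.
- k = 0.9: 0.64/0.73 = 0.88; times 1.046, 0.92.
- k = 0.8: 0.64/0.68 = 0.94; times 1.046, 0.98.

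In A the combined model is less precise than drug-only when r exceeds 0.91 (k = 1), lies between 0.76 and 0.96 (k = 0.9) or lies between 0.63 and 0.90 (k = 0.8). Because 1+k²−2kr − (1−r²) = (k−r)² ≥ 0, the loss never exceeds the period term's own 4.6%.

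**The case against.** The strongest objection is that the harm needs an input the documents do not supply: nothing shows drift in a three-week within-person change. A 0.5 SD step is nearly as large as the whole effect used here for power. This stands. A reader might infer that the drug-only test is invalid as written; with no drift it holds its level, both in the fixed splits and under the assumed rule.

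A reader might also take the fixed-split result, a rise of about 2 points whichever way the drift goes, as a bound for this trial. It is not one. Those splits are not response-driven, and under the assumed rule the effect is larger and depends on the sign of the drift. That rule is itself only one possibility.

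Next, section 12 promises a SAP, and sections 12.3 and the synopsis say how drug is coded without ruling out other terms. This is fair. But the SAP is due only before the final analysis, so it may come after the allocation has moved, and no further term is named now. Nor do the documents support an inference that terms would be chosen on seeing results: interim results are kept from the other study staff, and section 8.2 states "The study blind will be broken on completion of the clinical study and after the study database has been locked".

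The baseline covariate is partly a matter of preference, since subtraction is valid and the gain can be small or reverse. That also stands.

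On visits, section 4.1 suggests a baseline just before the three weeks of dosing, which points to Visit 4. But Visit 4's own list in section 10.4 names only social ability, and section 9.1.6 uses the social functioning heading for a bundle of measures, so the Appendix 1 row does not settle where SFS is taken. Finally, Appendix 1's Randomization mark at Visit 1 might look like a contradiction of section 4.1. It need not be, because that mark can refer to the crossover order. The date of the chronic-phase assignment is simply not stated.

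**Conclusion.** The point holds in conditional form, as a cheap improvement. The plan names drug as the only term while making allocation depend on interim results, so calibration of the primary test rests on the absence of drift in SFS change. The possible effect runs from none to substantial, with type I error of about 0.9% to 17% for steps of −0.5 to +0.5 SD under the one response-driven rule examined. Those figures rest on an assumed rule, assumed drift and normal errors, and are not a forecast for this trial. A period term brings the error rate back to about 5% in every case run. The gain in precision from baseline SFS is usual but not guaranteed. The gap in the definition of SFS change needs no assumption about drift: neither the baseline nor the final visit is settled.

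**What to change.** Before the first allocation change, state in section 12.3 and the synopsis, and carry into the promised SAP, a regression of SFS change (or final SFS) on three terms: drug, baseline SFS, and a factor for the allocation period in force when the chronic-phase assignment was made. Use grouped enrolment blocks if the ratio is updated often. State when that assignment is made. Name both the baseline and the final SFS visit, and bring sections 4.1, 5.1, 10.1 and 10.4 to 10.6 and Appendix 1 into line. Use the same model form for CAINS and the Hinting Task, each with its own baseline. A re-randomisation test is an optional sensitivity analysis.

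The cost is a few sentences and no additional data, provided the named visits are ones at which SFS is taken. With no drift, the period term raises variance by between 0.01% and 4.6% in the splits examined, at most about 2 points of power. The baseline covariate usually recovers this.
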